- 13) Known hypersensitivity or allergy to the IMP, its metabolites, or formulation excipients (microcrystalline cellulose, mannitol, croscarmellose sodium, magnesium stearate, polyvinyl alcohol, titanium dioxide, polyethylene glycol and talc)
- 14) History of hypersensitivity, anaphylactic reaction, Stevens-Johnson Syndrome, or toxic epidermal necrolysis response to sulfa drugs

Related to laboratory results:

- 15) Creatinine clearance < 30 mL/min (calculated using the Cockcroft-Gault method)
- 16) Clinically significant ALT/AST, as determined by the investigator
- 17) Clinically significant TB, as determined by the investigator

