6.1.2. Visit 2: Baseline Assessments, Randomization, and Treatment Assessments (Day 1)

6.1.2.1. Baseline Assessments

Visit 2 must be performed in clinic or in hospital and should occur within 24 hours of confirmation of the subject's eligibility. Samples and assessments performed at Screening (Visit 1) may not be used as Visit 2 Baseline assessments. Baseline (Visit 2) assessments should be performed in the following order and documented on Day 1 prior to IMP administration:

- FLU-PRO questionnaire

- Review of concomitant medications, mechanical ventilation (invasive and non-invasive of any duration), and supplemental O₂ use (≥ 2 L/min for >24 hours)
- Weight
- Vital Signs (body temperature, heart rate, respiratory rate, and blood pressure)
- O₂ saturation (on room air)
- Pre-dose blood draw for central and local laboratory analysis:
 - Safety Labs (hematology and serum chemistry to include to include WBC with differential, Hgb, platelets, BUN, creatinine, serum albumin, AST, ALT, ALP, and TB)
 - Serum antibody titer to RSV
 - Respiratory syncytial virus viremia
 - Local troponin testing
 - Local testing for lymphocyte count (if not obtained ≤ 6 days prior to Screening [Visit 1])
- Nasal samples (2 total, 1 from each nostril) for central laboratory virology testing
 - In Japan only, 1 swab sample will be collected at Baseline for central laboratory virology testing
- Urine or serum pregnancy test (for women unable to confirm menopause, hysterectomy and/or bilateral oophorectomy)
- 12-lead Pre-dose ECG

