6.11.6. Safety Labs

When available, the most recent laboratory values (obtained ≤ 6 days prior to Screening [Visit 1]) may be used for eligibility assessment, with the exception of RSV results and pregnancy testing. If an existing laboratory value is not available for eligibility assessment, the test will be performed using the local hospital laboratory. All blood samples will be collected pre-dose at all visits where IMP is administered.

Central laboratory testing of blood specimens for safety analysis will include WBC with differential, Hgb, platelets, BUN, creatinine, serum albumin, AST, ALT, ALP, and TB at Visits 2, 4, 6, 7, 8, 9, and 10 (Days 1, 5, 9, 13, 17, 22, and 28).

Any test showing an increase of serum ALT or AST $> 3 \times$ ULN or TB $> 2 \times$ ULN will be repeated within 48 to 72 hours for ALT, AST, ALP, and TB. If the repeat values are unchanged or are normalizing, monitoring will continue at weekly intervals until the results are acceptable or normalized. If any value has increased further, immediate close observation is required. If close monitoring is not possible, IMP will be discontinued.

Blood will also be drawn to monitor troponin levels pre-dose at Visits 2 and 8 (Days 1 and 17), and anytime at Visit 10 (Day 28). At each visit, the sample will be sent to the local lab at the clinical site for troponin analysis using the laboratory-based assay specific to the local trial site (eg, troponin I or T). Point-of-care "rapid" troponin tests are not acceptable for protocol-mandated troponin testing. The baseline troponin test must be pre-dose. However, troponin testing done for the purposes of patient care on the same day as a protocol-required test day may be used, provided the test is completed at the protocol-directed time and is a laboratory-based assay. Troponin results should be verified before the subject leaves the clinical site in case a troponin value is positive and further medical care is advised.

Blood specimens for serum creatinine will be collected 2 hours post-dose at Visits 2 and 6 (Days 1 and 9) from subjects participating in the PK subgroup only.

Urine or serum pregnancy tests will occur for all females of childbearing potential at Screening and at each dosing visit (Visits 2, 4, 6, 7, and 8) prior to administration of IMP.

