7.2.3. Liver-related Laboratory Evaluations

Liver-related abnormalities after initial study drug dosing will be examined and summarized using the number and percentage of subjects who were reported to have the following laboratory test values for post-baseline measurements:

- Aspartate aminotransferase (AST): (a) > 3 times of the upper limit of reference range (ULN); (b) > 5 x ULN; (c) > 10 x ULN; (d) > 20 x ULN
- Alanine aminotransferase (ALT): (a) > 3 x ULN; (b) > 5 x ULN; (c) > 10 x ULN; (d) > 20 x ULN
- AST or ALT: (a) > 3 x ULN; (b) > 5 x ULN; (c) > 10 x ULN; (d) > 20 x ULN
- Total bilirubin: (a) > 1 x ULN (b) > 2 x ULN
- Alkaline phosphatase (ALP) > 1.5 x ULN
- AST or ALT > 3 x ULN and total bilirubin: (a) > 1.5 x ULN; (b) > 2 x ULN
- AST or ALT > 3 x ULN, total bilirubin > 2 x ULN and ALP < 2 x ULN

The summary will include data from all post-baseline visits up to and including Day 28. For individual laboratory tests, subjects will be counted once based on the most severe post-baseline values. For both the composite endpoint of AST or ALT and total bilirubin, subjects will be counted once when the criteria are met at the same post-baseline visit date. The denominator is the number of subjects in the Safety Analysis Set who have nonmissing post-baseline values of all relevant tests at the same post-baseline visit date. A listing of subjects who met at least 1 of the above criteria will be provided.

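### The combined AST/ALT plus bilirubin rows of the liver table mix elevations present before dosing with new ones, and no planned table counts the new ones by arm

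*SAP*

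**What the plan says.** SAP 7.2.3 defines the liver summary by values after dosing. Results are "summarized using the number and percentage of subjects who were reported to have the following laboratory test values for post-baseline measurements". The three combined rows are AST or ALT > 3 x ULN with bilirubin > 1.5 x ULN, the same with bilirubin > 2 x ULN, and "AST or ALT > 3 x ULN, total bilirubin > 2 x ULN and ALP < 2 x ULN". The numerator rule for the combined rows is that "subjects will be counted once when the criteria are met at the same post-baseline visit date". The denominator is the Safety Analysis Set subjects with all relevant tests available on one post-baseline date. Neither rule mentions baseline.

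Eligibility is a matter of judgement. Protocol 4.3 excludes "Clinically significant ALT/AST, as determined by the investigator" and "Clinically significant TB, as determined by the investigator", with no multiple of ULN. Protocol 6.11.6 adds that "the most recent laboratory values (obtained ≤ 6 days prior to Screening [Visit 1]) may be used for eligibility assessment".

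The laboratory baseline in SAP 7.2.1 is the last measurement on or before the first dose. This is normally the Day 1 pre-dose sample, because Protocol 6.1.2.1 says that "Samples and assessments performed at Screening (Visit 1) may not be used as Visit 2 Baseline assessments". SAP 3.6.1 substitutes a screening value if the baseline value is missing.

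Elsewhere the SAP does use baseline: a rise of at least one grade for treatment-emergent laboratory abnormalities (7.2.2.1), a shift table for troponin (7.2.1.1), and new abnormalities plus a shift table for ECG (7.5).

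**The concern.** The combined rows are the planned by-arm summary of laboratory patterns that could be Hy's law cases. A reader of such a row looks at a handful of subjects and asks how many are new on treatment in each arm. As specified, the row cannot answer that, because one or two subjects with liver disease before dosing look the same as one or two new cases. HCT recipients can enter with raised liver tests, since the exclusions are not numeric. At stake is how readily a descriptive safety signal can be read, under a secondary objective that includes safety. No test or decision rule depends on it.

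**Working it through.** **Does the text leave the gap?** The documents state no figure on this point, so the first check sets the sections side by side.

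1. *Counting rule.* In SAP 7.2.3 the numerator needs the criterion on one post-baseline date and the denominator needs tests on one post-baseline date. Nothing removes or separates a subject who met the criterion before dosing.
2. *Can such a subject be dosed?* Yes, in two ways. The investigator may judge the values not clinically significant. Or the values may rise after the eligibility sample, which can be up to 6 days older than Screening: 6 days + 1 day from Day -1 to Day 1 = 7 days before dosing. Protocol 6.1.1 requires screening results to be reviewed before dosing. The Day 1 safety sample goes to the central laboratory (Protocol 6.11.6: "Central laboratory testing of blood specimens for safety analysis will include WBC with differential"), and no section requires that result before the dose.
3. *Does another table count new joint elevations?* The treatment-emergent tables (15.11.6.4.1.1 to 15.11.6.4.3) use toxicity grades. Protocol Appendix 4 grades each test alone and has no combined item. The chemistry tables (15.11.6.2.x) are also by single test. In the SAP 12.1 list, Table 15.11.6.5 is the only liver table.
4. *Single-test rows.* ALT/AST Grade 2 is > 2.5 to 5 x ULN, so a rise across 3 x ULN from 2.5 x ULN or below gains at least one grade and is caught as treatment-emergent. Only a start at > 2.5 to 3 x ULN that stays within Grade 2 escapes. For bilirubin, Grade 2 is > 1.5 to 2.5 x ULN, and only a start at > 1.5 to 2 x ULN that stays within Grade 2 escapes the 2 x ULN row. The gap there is narrow.

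**How large could it be?** Every rate below is an assumption. Let b be the share meeting the combined criterion at baseline and staying there. Let r be the rate of new combined elevations among the rest, taken as 3% against 1%. The 189 enrolled (SAP 1.3) are split 95 and 94.

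- Shown rate per arm = b + (1 - b) x r
- Expected pre-dose subjects = 189 x b
- Pre-dose share of the row = 189b / (95p1 + 94p2), where p1 and p2 are the shown rates

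Example, b = 1%: p1 = 0.01 + 0.99 x 0.03 = 3.97% and p2 = 0.01 + 0.99 x 0.01 = 1.99%. Subjects shown are 95 x 0.0397 = 3.77 and 94 x 0.0199 = 1.87. The pre-dose share is 1.89 / 5.64 = 33.5%.

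| b | Subjects shown | Risk difference (points) | Pre-dose subjects | Pre-dose share |
|---|---|---|---|---|
| 0 | 2.85 vs 0.94 | 2.00 | 0 | 0% |
| 0.25% | 3.08 vs 1.17 | 1.995 | 0.47 | 11.1% |
| 0.5% | 3.31 vs 1.41 | 1.99 | 0.95 | 20.0% |
| 1% | 3.77 vs 1.87 | 1.98 | 1.89 | 33.5% |
| 2% | 4.69 vs 2.80 | 1.96 | 3.78 | 50.4% |

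If no new injury occurs in either arm (r = 0), the chance that the row still shows someone is 1 - (1 - b)^189. The chance that the arms differ by two or more comes from independent Binomial(95, b) and Binomial(94, b) counts.

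| b | At least one shown | Arms differ by 2 or more |
|---|---|---|
| 0.25% | 38% | 4% |
| 0.5% | 61% | 11% |
| 1% | 85% | 25% |
| 2% | 98% | 42% |

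If only half of the baseline cases persist, read the line for half of b.

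A row limited to subjects negative at baseline would show 95 x (1 - b) x 0.03 against 94 x (1 - b) x 0.01. That is 2.84 vs 0.94 at b = 0.25% and 2.79 vs 0.92 at b = 2%.

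**The case against.** The strongest reply is that nothing in the plan is wrong. SAP 7.2.3 promises post-baseline values and delivers them, and the table title does not claim treatment emergence. SAP 7.2 plans no inferential laboratory statistics. Randomization balances baseline-positive subjects in expectation. All of this stands, and it is why the point is minor.

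New cases can also be found elsewhere. Listing 16.2.8.1.6 shows every subject who met a criterion, and the chronological chemistry listings show that subject's baseline. Protocol 7.5 requires an AE record when a laboratory abnormality independent of the underlying condition leads to dosing being stopped. Hy's law is a reason for considering discontinuation (Protocol 3.5), so some verified cases would appear by arm in Table 15.11.5.1. That route is partial: it needs dosing actually to be interrupted or stopped, and the last dose is on Day 17. The listings serve case review well but leave the by-arm count to be made by hand.

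A third reply is that the investigator exclusions and the pre-dose review of screening results may leave no such subject. That is possible, and the documents cannot settle it.

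Three stronger readings are tempting and are not supported. A reader might infer that the table is biased towards or against presatovir; the working shows the expected risk difference almost unchanged. A reader might extend the fault to the single-test rows; the graded tables already capture nearly all new crossings there. A reader might say that the table defeats the clinical verification in Protocol 3.5; that verification is a case-by-case review by the investigator with the Medical Monitor and does not use this table.

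**Conclusion.** The gap is real and minor. The combined rows do not separate pre-dose from new joint elevations, and no planned table counts the new ones by arm. Its size is unknown and is zero if no subject meets the criterion before dosing. Under the assumed 0.25% to 2% persistent baseline prevalence and new rates of 3% and 1%, about one in nine to one in two subjects in the row would be pre-dose cases. The cost is to the readability of a small descriptive count. The comparison between arms is not distorted in expectation, and the individual cases remain identifiable.

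**What to change.** In SAP 7.2.3 and Table 15.11.6.5:

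- Keep all existing rows.
- Show by arm how many subjects met each combined criterion at baseline.
- Add a row for new combined elevations under each of the three criteria. Limit numerator and denominator to subjects who did not meet the AST/ALT and bilirubin parts of that criterion at baseline.
- For the third criterion, ignore ALP when setting baseline status. Otherwise a subject with unchanged AST and bilirubin whose ALP falls from 2.1 to 1.9 x ULN would count as a new case. Protocol 6.1.1 also does not list ALP among the screening tests, so a substituted screening value might lack it.
- Define baseline as the last value on or before the first dose, with a screening value substituted if Day 1 is missing (SAP 7.2.1 and 3.6.1). Treat the subject as not meeting the criterion only if no pre-dose value exists.

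The cost is SAP wording and a few extra rows from data already collected. The drawback is that a subject positive at baseline who worsens on treatment appears only in the retained rows and the listing, which is why those must stay.

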7.3. Body Weight and Vital Signs

Body weight and vital signs (pulse rate, systolic and diastolic blood pressure, body temperature, and respiratory rate) at baseline and each post-baseline assessment, and change from baseline in body weight and vital signs at each post-baseline visit will be summarized for the safety analysis set using descriptive statistics (sample size, mean, SD, median, Q1, Q3, minimum, and maximum) by treatment group.

A baseline value will be defined as the last available value collected on or prior to the date/time of first dose of study drug. Change from baseline to a postbaseline visit will be defined as the postbaseline value minus the baseline value.

In the case of multiple values at an assessment, data will be selected for analysis as described in Section 3.8.4. No inferential statistics will be generated.

A by-subject listing of vital signs will be provided by subject ID number and visit in chronological order. Body weight will be included in the vital signs listing, if space permits. If not, they will be provided separately.

7.4. Prior and Concomitant Medications

Medications collected at screening and during the study will be coded using the current version of the World Health Organization (WHO) Drug dictionary. The medications will be categorized as prior or concomitant.

7.4.1. Prior Medications

Prior medications are defined as medications taken and stopped prior to or on the first dosing date or continued to take after the first dosing date of study drug.

Prior medications will be summarized by Anatomical Therapeutic Chemical (ATC) drug class and preferred name (using the number and percentage of subjects for each treatment group and overall). A subject reporting the same medication more than once will be counted only once when calculating the number and percentage of subjects who received that medication. The summary will be ordered alphabetically by ATC drug classes and then by preferred names in order of descending overall frequency within an ATC drug class. For drugs with the same frequency, sorting will be done alphabetically.

Summaries will be based on the Safety Analysis Set. No inferential statistics will be generated.

For the purposes of analysis, any medications taken and stopped prior to or on the first dosing date of study drug or continued to take after the first dosing date of study drug will be considered prior medications. Therefore, medications with a start date that is prior to the first dosing date of study drug will be included in the prior medication summary regardless when stop date is (as long as it is on or after the start date is). In addition, a medication with both start and stop dates that are the same as the first dosing date will be included in the summary. If a partial start date is entered, the month and year (if day is missing) or year (if day and month are missing) of the start date are after first dosing date will not be considered prior; otherwise, it is prior. Medications with completely missing start and stop dates will be included in the prior medication summary.

Prior ribavirin use will be summarized separately from other prior medications.

All prior medications (other than per-protocol study drugs) will be provided in a by-subject listing sorted by subject ID number and administration date in chronological order.

7.4.2. Concomitant Medications

Concomitant medications are defined as medications taken while a subject took study drug. Use of concomitant medications up to and including Day 28 visit will be summarized by ATC drug class and preferred name (using the number and percentage of subjects for each treatment

group). A subject reporting the same medication more than once will be counted only once when calculating the number and percentage of subjects who received that medication. The summary will be ordered alphabetically by ATC medical classes and then by preferred names in descending overall frequency within an ATC drug class. For drugs with the same frequency, sorting will be done alphabetically.

Summaries will be based on the Safety Analysis Set. No inferential statistics will be generated.

For the purposes of analysis, any medications started prior to or on the first dosing date of study drug and continued to take after the first dosing date, or started after the first dosing date but no later than last dosing date of study drug will be considered concomitant medications. Therefore, medications with a stop date that is on or prior to the date of first dosing date of study drug or a start date that is after the last dosing date of study drug will be excluded from the concomitant medication summary. If a partial stop date is entered, any medication with the month and year (if day is missing) or year (if day and month are missing) prior to the date of first study drug administration will be excluded from the concomitant medication summary. If a partial start date is entered, any medication with the month and year (if day is missing) or year (if day and month are missing) after the study drug stop date will be excluded from the concomitant medication summary. Medications with completely missing start and stop dates will be included in the concomitant medication summary.

Concomitant ribavirin use will be summarized separately from other concomitant medications.

All concomitant medications (other than per-protocol study drugs) will be provided in a by-subject listing sorted by subject ID number and administration date in chronological order.

7.5. Electrocardiogram Assessment

A 12-lead ECG will be performed at Visit 2 (Day 1), Visit 8 (Day 17), and Visit 10 (Day 28) and read by a certified cardiologist at a specialized central laboratory. Summaries of ECG assessments will be provided for the Safety Analysis Set

Number and percent of subjects with new ECG abnormalities at postbaseline visits including those assessments obtained for the purpose of standard of care will be summarize by treatments. Only subjects with baseline ECG assessments will be included in this analysis.

A shift table of the ECG assessment at each scheduled visit compared with baseline will be presented by treatment group using the following categories: normal, abnormal, or missing. The number and percentage of subjects in each cross-classification group of the shift table will be presented. Subjects with a missing value at baseline or postbaseline will not be included in the denominator for percentage calculation. No formal statistical testing is planned.

A by-subject listing for ECG assessments and ECG abnormalities will be provided by subject ID number and visit in chronological order.

No formal statistical testing is planned.

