6.11.8. Electrocardiogram (ECG)

As part of safety testing, at Visit 2 (Day 1) a pre-dose 12-lead ECG will be performed on the institution's equipment. A 12-lead ECG will also be performed pre-dose at Visit 8 (Day 17) and anytime at Visit 10 (Day 28). ECG results should be verified before the subject leaves the clinical site in case further medical care is advised. ECG testing done for the purposes of patient care on the same day as a protocol-required test day may be used, provided the test is completed at the protocol-directed time. Any additional ECG measures obtained for the purposes of patient care also require collection.

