8.6.4. Other Safety Evaluations

Vital signs and ECG data will be summarized using descriptive statistics by the observed data and by the change from Baseline at each time point. In comparison to pre-treatment (either screening or pre-dose on Study Day 1) values, vital signs and ECG measurements will additionally be summarized using pre-determined clinically relevant thresholds.

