7.7. Changes From Protocol-Specified Safety Analyses

No changes from protocol-specified safety analyses.

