11. SAP REVISION

Revision Date (dd month, yyyy)	Section	Summary of Revision	Reason for Revision
10 October 2017	Throughout the document	Made minor editorial changes	The editorial, administrative, and formatting changes were made to Glied standard template updates, where appropriate, to improve clarity and consistency.
10 October 2017	Section 3.1.3	Updated IPD criteria	This section was updated to align with the IPD amendment and to provide the details.
10 October 2017	Section 3.8.4	Added texts to define the baseline and postbaseline values when multiple records exist	This section was revised to provide more details and clarification.
10 October 2017	Section 4.1	Added two more categories in subject disposition summary	The addition was to provide extra information for subjects enrolled in the Extended Viral Load monitoring period.
10 October 2017	Section 4.2.2	Added by-subject listing of study drug administration and drug accountability	The listings were included to provide individual level data.
10 October 2017	Section 5.3	Updated HCT-specific medical history summary	This section was revised to provide more clarification that the disease-specific summary will be provided by treatment and general medical history will not be coded.
10 October 2017	Section 6.4.2	Removed the related analyses for RSV log ₁₀ viral load in the blood	No RSV viral load data in the blood are available due to a lack of validated assays
10 October 2017	Section 7.1.6.1	Added more TEAE tables and listings	The additional AE summaries were included to provide complete safety assessments.
10 October 2017	Section 7.2.1.1	Updated analysis for troponin data	This section was revised to provide the details and clarification for troponin assessment
10 October 2017	Section 7.1.7	Added cardiac adverse event of interest	The cardiac AE of interest were evaluated to comply with FDA mandated cardiac monitoring requirements
10 October 2017	Section 7.2.3	Added liver related laboratory evaluation	The evaluation was added in order to comply with regulatory requirements.
10 October 2017	Section 7.5	Updated analysis for ECG data	This section was revised to provide the details and clarification for ECG

			assessment
10 October 2017	Section 13	Updated Table of Contents for statistical tables, figures, and listings	The Table of Contents was updated to include additional analyses results.
10 October 2017	Appendix 3 and Appendix 4	Added SAS example codes	The example codes were provided for analyses.

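### The SAP omits three of the four ECG and vital-sign summaries promised in the protocol, plans no summary of any ECG interval, and declares no change

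*SAP*

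**What the plan says.** Protocol 8.6.4 covers ECG and vital signs together. For every time point, it states that "Vital signs and ECG data will be summarized using descriptive statistics by the observed data and by the change from Baseline". It then adds, relative to pre-treatment values, that "vital signs and ECG measurements will additionally be summarized using pre-determined clinically relevant thresholds".

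For ECG, SAP 7.5 plans three outputs:

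- "Number and percent of subjects with new ECG abnormalities at postbaseline visits", including ECGs done for standard of care, in subjects who have a baseline ECG.
- "A shift table of the ECG assessment at each scheduled visit compared with baseline will be presented by treatment group". Its only classes are an overall call of normal or abnormal, and a third class for missing results.
- A by-subject listing of assessments and abnormalities.

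The shells in SAP 12 match: tables 15.11.9.1 and 15.11.9.2, listing 16.2.8.3, and no ECG figure.

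For vital signs, SAP 7.3 gives descriptive statistics of observed values and change from baseline by visit, with tables and figures 15.11.7.1.1 to 15.11.7.1.5. It names no thresholds.

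SAP 7.7 reads: "No changes from protocol-specified safety analyses". The SAP revision log describes the update of 7.5 only as detail and clarification.

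**The concern.** The protocol commits to measuring ECG change on a numeric scale and against set limits. The SAP reduces the ECG to an overall normal or abnormal call and does not disclose that it has done so. An overall call has no mean, no SD and no change from baseline, so the plan would give no size or direction for a shift in any interval.

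The background makes intervals relevant without proving a problem. Protocol 1.2.3 reports a hERG IC50 and slightly higher PR and QTc values in dogs, attributed there to lower heart rate. Protocol 1.2.4.1 reports no clinically significant increase in PR, QRS, QT or QTcF in healthy subjects. An interval summary in transplant recipients would add to that record.

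The thresholds have a further problem. They were to be set in advance, but neither Protocol 8.6.4 nor the SAP states them. Thresholds chosen after unblinding would be post hoc.

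**Working it through.** The plan states no figure to reproduce here. The check sets the protocol's promises against the SAP text and shells.

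| Promised in Protocol 8.6.4 | In the SAP? | Where |
|---|---|---|
| ECG: observed values and change from baseline | No | 7.5; tables 15.11.9.1, 15.11.9.2 |
| ECG: thresholds | No | 7.5; same tables |
| Vital signs: observed values and change from baseline | Yes | 7.3; five tables, five figures |
| Vital signs: thresholds | No | 7.3; no table |

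**Count.** 4 promised − 1 kept = 3 absent. Two ECG tables are planned, both are categorical, and none summarises an interval.

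**Oxygen saturation.** Table 15.9.3.5 counts subjects whose saturation falls to 88% or below. It is an efficacy table in the Full Analysis Set. Protocol 6.11.4 defines vital signs as temperature, heart rate, respiratory rate and blood pressure, so this table does not fill the fourth row.

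**Does the promise mean intervals?** Protocol 8.6.4 does not name PR, QRS or QTc, so this is an inference. It is a reasonable one: the glossary defines these terms, the Phase 1 summary reports them, and Protocol Appendix 4 grades PR and QTc numerically. Descriptive statistics and change from baseline also need a number to work on.

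**What the planned tables can show.** A subject whose ECG is abnormal at baseline and afterwards sits in the same shift cell however far an interval has moved. The new-abnormality count can pick up some of these subjects, because it requires a baseline ECG but not a normal one. It gives no size or direction.

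**What restored tables could show.** Protocol 6.11.8 places the post-baseline ECGs pre-dose on Day 17 and at any time on Day 28. On the nominal schedule these fall as follows:

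- Day 17 is 17 − 13 = 4 days = 96 hours after the previous dose.
- Day 28 is 28 − 17 = 11 days = 264 hours after the last dose.

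With the half-life of about 36 hours in Protocol 1.2.4.1, that is 96/36 = 2.7 and 264/36 = 7.3 half-lives. Neither ECG is near peak concentration.

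**Redaction.** Protocol 8.6.4 and SAP 7.3, 7.5 and 7.7 show no blacked-out text, so redaction does not explain the gap.

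**The case against.** The best defence is that cardiac safety is not left unexamined. Numeric vital-sign summaries are kept in full. The new-abnormality count takes in standard-of-care ECGs and subjects with abnormal baselines. SAP Appendix 2 captures QT-related adverse events through a QT-prolongation query and ECG-investigation terms, and these feed tables 15.11.2.4 and 15.11.4.4. The scheduled ECGs are also poorly timed for detecting an effect at peak. All of this stands, and it limits the consequence. It does not make the SAP match Protocol 8.6.4 or make SAP 7.7 correct.

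A reader might infer more than the documents support:

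- **That a regulatory cardiac-monitoring mandate is breached.** The SAP revision log does use the words "comply with FDA mandated cardiac monitoring requirements", but as the reason for adding cardiac adverse events of interest, which the SAP delivers. Neither document says the mandate requires interval statistics.
- **That the documents contradict each other on ECG reading.** The protocol says "a pre-dose 12-lead ECG will be performed on the institution's equipment", while SAP 7.5 refers to reading at a central laboratory. The first concerns recording and the second reading; they are compatible.
- **That the Appendix 4 PR and QTc grades are never tabulated.** Investigators grade adverse events on that scale and SAP 7.1.6.1 tabulates them by maximum severity, so a reported PR or QTc event would appear with its grade. What is missing is any classification of the measured intervals.
- **That precise interval data are being discarded.** The documents give no SD for QTc change. With 189 subjects split evenly (94.5 per arm), every subject evaluable, and assumed SDs of 15, 20 and 25 ms, 1.96 × SD × √(2/94.5) gives 95% half-widths of 4.3, 5.7 and 7.1 ms. Those inputs are assumptions, and the documents do not say whether interval values are in the database.

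**Conclusion.** The point holds in this form. Three of the four ECG and vital-sign summaries promised in Protocol 8.6.4 are absent from the SAP: numeric ECG, threshold ECG and threshold vital signs. The statement in SAP 7.7 is wrong as written. No planned table or figure summarises an ECG interval.

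This is more than a lack of detail, because carrying out the SAP exactly would leave the size and direction of any interval change unreported. It should be corrected, but it touches no primary or secondary efficacy endpoint, and adverse-event reporting of QT-related events is intact. The part about PR, QRS and QTc rests on reading the protocol's reference to ECG measurements as including intervals. The omission itself, and the error in SAP 7.7, do not depend on that reading.

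**What to change.** - **SAP 7.5:** add observed values and change from baseline for the ECG intervals at Days 17 and 28 by arm, and counts against thresholds fixed before unblinding. The PR and QTc categories in Protocol Appendix 4 are one available set. If they are used, the SAP needs rules for values that fall between the QTc grades and for the Grade 1 increase criterion, which as written takes in any rise under 0.03 s. A between-arm 95% CI is optional, since the protocol does not promise one.
- **SAP 7.3:** state the vital-sign thresholds and add the table.
- **SAP 7.7:** replace the statement of no change with an accurate one.
- **If interval values are not in the database** and cannot be extracted from tracings and reports (Protocol 6.11.9.2 provides for collecting these), record and justify the removal in SAP 7.7.

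The cost is SAP text, a few tables and possibly some data entry. The SAP should also state the limit of what is gained: with a pre-dose Day 17 ECG and a post-treatment Day 28 ECG, the summaries cannot exclude an effect at peak concentration.
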